5.2. Baseline Disease Characteristics

The following baseline disease characteristics will be summarized:

- HIV-1 RNA categories (copies/mL): (a) < 50, (b) ≥ 50
- CD4+ cell count (/ μ L)
- CD4+ cell count categories (/ μ L): (a) < 50, (b) ≥ 50 to < 200, (c) ≥ 200 to < 350, (d) ≥ 350 to < 500, and (e) ≥ 500
- CD4 percentage (%)
- Mode of infection (HIV risk factors)
- HIV disease status
- HBV surface antigen status
- HIV/HBV coinfection at baseline, which is defined as:

Positive HBsAg (HBV Surface Antigen) on or prior to the first dose date, or

Negative HBsAg, negative HBsAb (HBV Surface Antibody), positive HBcAb (HBV Core Antibody), and Quantifiable HBV DNA (ie, HBV DNA >20 IU/mL) on or prior to the first dose.

- HCV antibody status
- Medical history: diabetes (Yes/No), hypertension (Yes/No), cardiovascular disease (Yes/No), and hyperlipidemia (Yes/No) (See [Appendix 5](#) for additional details)
- Tobacco smoking history (never smoker, former smoker, current smoker)

- Relative with myocardial infarction or stroke before 50 years-old
- eGFR_{CG} (mL/min)
- estimated GFR using the CKD-EPI formula, eGFR_{CKD EPI, cysC} (mL/min/1.73 m²)
- ARV regimen at study entry (see [Appendix 7](#) for additional details)

No inferential statistics will be provided.

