7.1.7.2. Cardiovascular or Cerebrovascular Events

Preferred terms for cardiovascular or cerebrovascular events are from relevant Standardised MedDRA Query (SMQ). The selected PT listing was provided by Gilead PVE and reviewed by Gilead medical monitors, which is the same PT listing used to search “Cardiovascular Disease” medical history (see details in [Appendix 3](#)).

The number and percentage of subjects with treatment-emergent cardiovascular or cerebrovascular events and serious cardiovascular or cerebrovascular events by PT will be summarized based on the safety analysis set. A data listing of cardiovascular or cerebrovascular events will be provided.

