Appendix 5. Medical History

Number and percentage of subjects with selected medical history of Diabetes Mellitus, Hypertension, Cardiovascular Disease, and Hyperlipidemia will be summarized by treatment as baseline disease characteristics. A subject who had medical history of one of these diseases is a subject who experience at least one of the following events:

- At least 1 medical history record with MedDRA PT (mh.MDRPT) in the selected PT listing for the corresponding disease with start date on or prior to the first dose date.
- At least 1 adverse event record with MedDRA PT (ae.MDRPT) in the selected PT listing for the corresponding disease with start date on or prior to the first dose date.
- At least 1 concomitant medications record with medication class and indication in the following selected listing for the corresponding disease with start date on or prior to the first dose date.

If the start date is incomplete but the month and year (or year alone) of the start date is the same as or before the month and year (or year alone) of the first dosing date of study drug, then the event will be included. If the start date is completely missing, the event will be included.

Four variables (ie, DIABETES, HTENSION, CARDDIS, and HLIPDEM) will be added to raw Medical History and Adverse Events datasets. A medical history or an adverse event record will be flagged for a disease of interest if its MedDRA PT included in the pre-specified PT list for the corresponding disease of interest, which include all PTs from the narrow or broad search of the following SMQs under MedDRA 23.0 provided by Gilead DSPH and reviewed by Gilead medical monitors.

Disease of Interest	SMQ Source
Diabetes Mellitus (DIABETES)	Hyperglycaemia/new onset diabetes mellitus (SMQ) Narrow Scope Term
Hyperlipidemia (HLIPDEM)	Dyslipidaemia (SMQ)
Hypertension (HTENSION)	Hypertension (SMQ)
Cardiovascular disease (CARDDIS)	Ischaemic central nervous system vascular conditions (SMQ) Narrow Scope Term
	Myocardial infarction (SMQ) Narrow Scope Term
	Other ischaemic heart disease (SMQ) Narrow Scope Term

Similarly, four variables (ie, DIABETES, HTENSION, CARDDIS, and LIPMOD) will be added to raw Concomitant Medication dataset. A concomitant medication record will be flagged for a disease of interest if its medication preferred term and indication included in the following listing for the corresponding disease of interest.

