	Indication (CMINDC)	Preferred Term
Hyperlipidemia (LIPMOD)		
1	DYSLIPEMIA	ATORVASTATIN
2	DYSLIPIDEMIA	ATORVASTATIN
3	HIPERCHOLESTEROLEMIA	ATORVASTATIN
4	HIPERCOLESTEROLEMIA	ATORVASTATIN
5	HYPERCHOLESTEROLEMIA	ATORVASTATIN
6	HYPERLIPEMIA	ATORVASTATIN
7	HYPERLIPIDAEMIA	ATORVASTATIN
8	HYPERTRIGLYCERIDEMIA	ATORVASTATIN
9	MILD HYPERCHOLESTEROLEMIA	ATORVASTATIN
10	DISLIPEMIA	ATORVASTATIN CALCIUM
11	HYPER COLESTEROLEMY	ATORVASTATIN CALCIUM
12	HYPERCHOLESTEROLEMIA	ATORVASTATIN CALCIUM
13	HYPERCHOLESTEROLEMIE	ATORVASTATIN CALCIUM
14	HYPERTRIGLYCERIDEMIA	GEMFIBROZIL
15	HYPERTRIGLYCERIDEMIA	OMEGA 3 TRIGLYCERIDES
16	DISLIPEMIA MIXTA	PITAVASTATIN
17	ELEVATED LIPIS	PRAVASTATIN
18	ESSENTIAL HYPERCHOLESTEROLEMIA	PRAVASTATIN
19	HYPERLIPEMIA	PRAVASTATIN
20	HYPERCHOLESTEROLEMIA	PRAVASTATIN SODIUM
21	DYSLIPIDEMIA	ROUVASTATIN
22	HYPERCHOLESTEROLEMIA	ROUVASTATIN
23	HIPERCOLESTEROLEMIA	ROUVASTATIN
24	SMALL FIBROUS PLATE	ROUVASTATIN
25	CARDIOVASCULAR PREVENTION	ROUVASTATIN CALCIUM
26	DYSLIPIDEMIA	ROUVASTATIN CALCIUM
27	HIPERCHOLESTERIEMIA	ROUVASTATIN CALCIUM
28	HIPERCHOLESTEROLEMIA	ROUVASTATIN CALCIUM
29	HIPERCHOLESTEROLEMY	ROUVASTATIN CALCIUM
30	HIPERCHOLESTEROLEMIA, CONTINUED ELEVATED LEVELS OF LDL	SIMVASTATIN
31	HYPERLIPEMIA	SIMVASTATIN

	Indication (CMINDC)	Preferred Term
Diabetes Mellitus (DIABETES)		
1	DIABETES MELLITUS TYPE 2	DAPAGLIFLOZIN;METFORMIN
2	MELLITUS DIABETES	EMPAGLIFLOZIN
3	DIABETES MELLITUS	GLICLAZIDE
4	DIABETES MELLITUS	INSULIN GLARGINE
5	MELLITUS DIABETES TYPE II	LINAGLIPPTIN
6	DIABETES	METFORMIN
7	DIABETES MELLITUS	METFORMIN
8	DIABETES MELLITUS TYPE 2	METFORMIN
9	HYPERGLYCEMIA	METFORMIN
10	MELLITUS DIABETES	METFORMIN
11	TYPE 2 DIABETES MELLITUS	METFORMIN
12	DIABETES	METFORMIN EMBONATE
13	DIABETES	METFORMIN HYDROCHLORIDE
14	METABOLE SYNDROME (INSULIN RESISTANCE)	METFORMIN HYDROCHLORIDE
15	MELLITUS DIABETES	METFORMIN HYDROCHLORIDE;SITAGLIPPTIN PHOSPHATE

	Indication (CMINDC)	Preferred Term
	Cardiovascular disease (CARDDIS)	
1	AORTIC VALVE DISEASE	ACENOCOUMAROL
2	ACUTE MYOCARDIAL INFARCTION	ACETYLSALICYLATE LYSINE
3	BIFEMORAL ARTERY BYPASS SURGERY	ACETYLSALICYLATE LYSINE
4	CARDIOPATHY	ACETYLSALICYLATE LYSINE
5	STROKE	ACETYLSALICYLIC ACID
6	MYOCARDIAL INFARCTION	ACETYLSALICYLIC ACID;CLOPIDOGREL BISULFATE
7	ISCHEMIA CARDIOMYOPATHY	AMILORIDE;HYDROCHLOROTHIAZIDE
8	ARYTHMIA	AMIODARONE
9	ATRIAL FIBRILLATION	AMIODARONE
10	CARDIAC RHYTHM DISORDER	AMIODARONE
11	ANGINA	AMOXICILLIN TRIHYDRATE;CLAVULANATE POTASSIUM

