12	INFECTIOUS ENDOCARDITIS ON A PROSTHETIC VALVE WITHOUT MICROBIOLOGICAL AFFILIATION, CARDIOEMBOLISM, AND RECURRENT ACUTE CEREBRAL VASCULAR DISEASE.	AMPICILLIN
13	ATRIAL FIBRILLATION	ATENOLOL
14	HYPERTENSION	ATENOLOL
15	ISCHEMIC HEART DISEASE	ATENOLOL
16	ISCHEMIC STROKE IN THE TERRITORY OF LEFT MIDDLE CEREBRAL ARTERY	BEMIPARIN SODIUM
17	ARYTHMIA	BISOPROLOL FUMARATE
18	PROPHYLAXIS FOR MYOCARDIAL INFARCTION	BISOPROLOL FUMARATE
19	ISCHEMIA CARDIOMYOPATHY	CLOPIDOGREL
20	CARDIOPATHY	CLOPIDOGREL BISULFATE
21	INFECTIOUS ENDOCARDITIS ON A PROSTHETIC VALVE WITHOUT MICROBIOLOGICAL AFFILIATION, CARDIOEMBOLISM, AND RECURRENT ACUTE CEREBRAL VASCULAR DISEASE.	CLOXACILLIN
22	ATRIAL FIBRILLATION	DABIGATRAN
23	INFECTIOUS ENDOCARDITIS ON A PROSTHETIC VALVE WITHOUT MICROBIOLOGICAL AFFILIATION, CARDIOEMBOLISM, AND RECURRENT ACUTE CEREBRAL VASCULAR DISEASE.	DALBAVANCIN
24	INFECTIOUS ENDOCARDITIS ON A PROSTHETIC VALVE WITHOUT MICROBIOLOGICAL AFFILIATION, CARDIOEMBOLISM, AND RECURRENT ACUTE CEREBRAL VASCULAR DISEASE.	DAPTOMYCIN
25	MYOCARDIAL INFARCTION	DOXAZOSIN MESILATE

	Indication (CMINDC)	Preferred Term
26	ISCHEMIA CARDIOMYOPATHY	ENALAPRIL
27	ATRIAL FIBRILLATION	ENOXAPARIN SODIUM
28	ARRHYTHMIA	FLECAINIDE
29	ACUTE PULMONARY ODEMA	FUROSEMIDE
30	CARDIAC ARREST	FUROSEMIDE
31	PEDAL ODEMA	FUROSEMIDE
32	INFECTIOUS ENDOCARDITIS ON A PROSTHETIC VALVE WITHOUT MICROBIOLOGICAL AFFILIATION, CARDIOEMBOLISM, AND RECURRENT ACUTE CEREBRAL VASCULAR DISEASE.	HEPARIN
33	STROKE	HEPARIN
34	ISCHEMIC HEART DISEASE	HYDROCHLOROTHIAZIDE
35	MYOCARDIAL INFARCTION	LERCANIDIPINE
36	ISCHEMIA CARDIOMYOPATHY	OMEPRAZOLE
37	CARDIOVASCULAR PREVENTION	PRASUGREL HYDROCHLORIDE
38	ARTERIOPATHY	PRAVASTATIN
39	HEART RHYTHME DISTURBANCE	PROPAFENONE
40	CARDIOVASCULAR PREVENTION	RAMIPRIL
41	LOWER LIMB ODEMA	RAMIPRIL
42	ACUTE MYOCARDIAL INFARCTION	ROSUVASTATIN CALCIUM
43	CARDIOVASCULAR PREVENTION	ROSUVASTATIN CALCIUM
44	PROPHYLAXIS FOR MYOCARDIAL INFARCTION	ROSUVASTATIN CALCIUM
45	ATRIAL FIBRILLATION	SOTALOL HYDROCHLORIDE
46	ARYTHMIA	WARFARIN SODIUM
47	ATRIAL FIBRILLATION	WARFARIN SODIUM

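### The medication list behind the baseline cardiovascular-disease flag has hypertension, oedema, valve and rhythm rows outside the SAP's three ischaemic SMQs, so the flag can overstate cardiovascular history and miss atenolol-treated hypertension

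*SAP*

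**What the plan says.** SAP section 5.2 reports diabetes, hypertension, cardiovascular disease and hyperlipidemia as yes/no baseline characteristics and refers to Appendix 5 for the derivation.

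Appendix 5 states the rule as follows: "A subject who had medical history of one of these diseases is a subject who experience at least one of the following events". The three sources are a medical-history preferred term, an adverse-event preferred term, and a medication record, each starting on or before the first dose. The third is worded "At least 1 concomitant medications record with medication class and indication in the following selected listing". The programming sentence later in the appendix reads: "A concomitant medication record will be flagged for a disease of interest if its medication preferred term and indication included in the following listing".

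In the two preferred-term sources, cardiovascular disease means three SMQs, all narrow scope: ischaemic central nervous system vascular conditions, myocardial infarction, and "Other ischaemic heart disease (SMQ) Narrow Scope Term".

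The medication source is a printed list of 47 CARDDIS rows. Among its indications are "LOWER LIMB ODEMA" (row 41, ramipril), hypertension (row 14, atenolol) and angina paired with "AMOXICILLIN TRIHYDRATE;CLAVULANATE POTASSIUM" (row 11). The hypertension list (HTENSION) has 57 rows.

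For on-study cardiovascular or cerebrovascular events, SAP section 7.1.7.2 uses a preferred-term list only, "which is the same PT listing used to search" cardiovascular medical history.

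**The concern.** One yes/no variable is built from sources that do not share a definition. Two sources are restricted to ischaemic cardiac and cerebral disease. The third admits indications that are not ischaemic and, in the case of hypertension, indications that belong to a different variable in the same table. Because any one source is enough, the medication list can only add subjects to the cardiovascular count.

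The trial exists to describe B/F/TAF in people aged 65 or over, and comorbidity at baseline tells a reader which older patients the results describe. An inflated cardiovascular percentage, or a hypertension percentage that is too low, would misdescribe them. The baseline definition is also wider than the on-study event definition, although section 7.1.7.2 presents the two as using the same preferred-term list. A reader who sets baseline history against on-study events would be comparing different things.

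**Working it through.** The plan gives no figure to reproduce. The check is a row-by-row comparison of the CARDDIS list with the three SMQ titles, followed by a conversion to percentage points.

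**Inputs**
- CARDDIS medication list: 47 rows (SAP Appendix 5).
- HTENSION medication list: 57 rows (SAP Appendix 5).
- Denominator: 86 subjects in the Safety Analysis Set (SAP Appendix 7, disposition mock-up). Section 5.1 names this set for baseline summaries; I assume that 5.2 uses it too.
- Matching rule: preferred term together with indication. Appendix 5 also mentions medication class, but the lists give no class, so only the preferred-term rule can be applied.

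**Step 1. Rows outside the three ischaemic SMQ titles**

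| Indication | CARDDIS rows | Count |
|---|---|---|
| Rhythm disorder, including atrial fibrillation | 8, 9, 10, 13, 17, 22, 27, 28, 39, 45, 46, 47 | 12 |
| Oedema (acute pulmonary, pedal, lower limb) | 29, 31, 41 | 3 |
| Aortic valve disease | 1 | 1 |
| Hypertension (atenolol) | 14 | 1 |
| Total | | 17 |

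17/47 = 36.2% of rows.

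**Step 2. Ambiguous rows, not counted above**
- Row 11: angina with an antibiotic. The indication is ischaemic as recorded; the drug makes that reading doubtful.
- Rows 37, 40 and 43 (cardiovascular prevention) and rows 18 and 44 (prophylaxis for myocardial infarction): the text does not say whether an event had already occurred.

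That is 1 + 5 = 6 rows. The other 47 − 17 − 6 = 24 rows are left alone here, although a few carry broad indications such as cardiopathy or arteriopathy.

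**Step 3. The atenolol pair**

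Atenolol appears in 0 of the 57 HTENSION rows. Other beta-blockers given for hypertension are there (bisoprolol, celiprolol, nebivolol). So are acetylsalicylic acid, alfuzosin, edoxaban and phenprocoumon where the recorded indication is hypertension. The HTENSION list therefore follows the indication, and the atenolol row breaks that pattern. If this record is the subject's only evidence, the result is CARDDIS = Yes and HTENSION = No, and two lines of the table are wrong.

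**Step 4. Consistency across sources**

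Atrial fibrillation with warfarin (row 47) sets the flag. Atrial fibrillation recorded only in medical history matches none of the three SMQ titles. The classification then depends on whether a listed drug was recorded, not on the disease.

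**Step 5. Size per subject**

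If k subjects are positive only through rows of this kind, the cardiovascular percentage is too high, against the SMQ definition, by 100 × k/86. The documents do not give k; the values below are assumptions.

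| k | Percentage points |
|---|---|
| 1 | 1.2 |
| 2 | 2.3 |
| 3 | 3.5 |
| 5 | 5.8 |
| 10 | 11.6 |

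**The case against.** The strongest defence is that the medication list is one of the three components of the SAP's definition, not a departure from it. The sponsor's medical monitors reviewed it, and the variable is labelled cardiovascular disease, not ischaemic disease. On that view the rhythm and valve rows, 13 of the 17, reflect a choice of breadth. This partly stands: a broader definition would be legitimate. But it would have to apply to medical history and adverse events as well, and it does not. Nor does breadth explain why hypertension treated with atenolol sits in the wrong list.

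Several stronger readings are tempting, and the documents do not support them:

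- **A reader might infer that cardiovascular history is in fact overstated.** That needs a subject with such a record starting by the first dose and no other qualifying evidence. No subject-level data are given, and the number could be zero.
- **A reader might take 17 of 47 as a rate of misclassification.** Rows are not subjects: five rows (12, 21, 23, 24, 32) share one identical endocarditis indication.
- **A reader might take the prevention rows as primary prevention, and so as errors.** The list does not say primary. Treatment after an ischaemic event is not excluded, and such a subject would be flagged correctly.
- **A reader might take row 11 as a certain error.** That angina here is not cardiac is an inference from the antibiotic; the list does not say so.
- **A reader might conclude that every atenolol-treated hypertensive is missed.** Hypertension can still be set by a Hypertension SMQ term in medical history or adverse events, or by any listed HTENSION pair.

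The reach is also limited. SAP sections 3.3, 3.4 and 7.7 plan no stratification or subgroup analysis, and on-study events use the narrow preferred-term list.

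**Conclusion.** The concern holds as a minor error in a stated rule. Of the 47 CARDDIS medication rows, 17 fall outside the concept used by the other two sources, and 6 more need review. The flag can overstate cardiovascular history relative to the three SMQs, and it is inconsistent across sources for rhythm disorders. The hypertension and atenolol pair is misfiled; it does harm only where it is the sole evidence of hypertension.

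The number of subjects affected is unknown. Each one moves the affected baseline percentage by 1.2 points on 86. No efficacy result or on-study event count depends on the flag; the effect is confined to the baseline disease characteristics table.

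This rests on three assumptions: records are matched on preferred term and indication; the denominator is the Safety Analysis Set; and the SMQ titles describe their content, since the SAP does not reproduce the preferred terms.

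**What to change.** In SAP Appendix 5:

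1. Move the hypertension and atenolol pair (row 14) from CARDDIS to HTENSION.
2. Remove the oedema rows (29, 31, 41) from CARDDIS.
3. Choose one definition of cardiovascular disease for all three sources. Either remove the rhythm and valve rows so that the medication list matches the three SMQs, or adopt a broader definition, state it, and extend the medical-history and adverse-event searches to match.
4. Check row 11 and rows 18, 37, 40, 43 and 44 against the subject's medical history before keeping them. A rule that deletes rows by indication alone would keep row 11, so that row needs an individual check.
5. Keep the medication source. Dropping it would lose valid rows for stroke, myocardial infarction and ischaemic heart disease (for example 2, 5, 6, 15, 16) and could cause undercounting.

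The cost is a lookup-table edit, a review of six rows and a rerun of one baseline table; the broader option in step 3 also needs a wider preferred-term search. If the SAP is already final, its Introduction gives the route: document the change in the clinical study report.

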Appendix 6. Determining Missing and Virtual Visits due to COVID-19

This appendix describes the site collection of COVID-19 data as it pertains to missed/virtual visits and the data processing algorithm used to determine which visits were missing and which visits were virtual.

Data collection

A COVID-19 supplement to the eCRF Completion Guidelines (CCG) was provided by data management to instruct clinical trial sites with respect to data entry expectations pertaining to scenarios related to the COVID-19 pandemic. If a visit was missed, sites should enter “Visit missed due to COVID-19.” If a visit which was to be conducted in-person was conducted virtually, sites should enter “Virtual visit due to COVID-19.”

Determination of Missed and Virtual visits

Natural Language Processing (NLP) was used to search the CRF comment fields to identify instances of “COVID-19” (or synonyms, see [Table X 1](#)) and “Virtual” (or synonyms, see [Table X 1](#)). The search terms are maintained in a global lookup and can be modified and/or corrected to tune the NLP model. For each comment field the following algorithm was applied:

STEP 1: Eliminate extraneous text from each comment field, e.g. “and”, “or”, “for”, etc. This is done using the list of extraneous terms given in [Table X 2](#).

STEP 2: Check each of the remaining comment text strings against the “COVID-19” terms and “Virtual” terms with the Levenshtein distance, using SAS function COMPGED (Computes a generalized edit distance using the Levenshtein operations to compute/summarize the degree of difference between two text strings):

- i) If Levenshtein distance < 149 for any of the “COVID-19” terms then COVIDFL = 1, else COVIDFL = 0
- ii) If Levenshtein distance < 149 for any of the “Virtual” terms then VIRTFL = 1, else VIRTFL = 0

STEP 3: For any comments with COVIDFL = 1, assign “Missed visit” or “Virtual visit” as follows

- i) IF COVIDFL = 1 and the visit date is missing then result is ‘Missed Visit’
- ii) IF COVIDFL = 1 and VIRTFL = 1 then result is ‘Virtual Visit’
- iii) Otherwise result is missing

Examples of search terms for “COVID-19” and “Virtual” used to identify missed and virtual visits.

Table X 1.

Search terms for “COVID-19”	Search terms for “Virtual”
COVID	VIRTUAL
CORONA	TELEMED
CORONAVIRUS	TELEHEALTH
PANDEMIC	TELEPHONE
OUTBREAK	REMOTE
CRISIS	TELEMEDICINE
LOCKDOWN	TELECONSULTAION
QUARATINE	TELEPHONICALLY
SHELTER	PHONE
	HOME VISIT
	ZOOM
	SKYPE

Examples of extraneous text terms to eliminate from the comment fields.

Table X 2.

a	down	in	she'd	until
about	during	into	she'll	up
above	each	is	she's	very
after	few	it	should	was
again	for	its	so	we
against	from	it's	some	we'd
all	further	itself	such	we'll
am	had	i've	than	were
an	has	let's	that	we're
and	have	me	that's	we've
any	having	more	the	what
are	he	most	their	what's
as	he'd	my	theirs	when
at	he'll	myself	them	when's

be	her	nor	themselves	where
because	here	of	then	where's
been	here's	on	there	which
before	hers	once	there's	while
being	herself	only	these	who
below	he's	or	they	whom
between	him	other	they'd	who's
both	himself	ought	they'll	why
but	his	our	they're	why's
by	how	ours	they've	with
could	how's	ourselves	this	would
did	i	out	those	you
do	i'd	over	through	you'd
does	if	own	to	you'll
doing	i'll	same	too	your
down	i'm	she	under	you're
	you've	yourself	yourselves	yours

Appendix 7. Programming Specification

1. Subject disposition mockup table

	B/F/TAF
Subjects Screened	xx
Screen Failure Subjects Who Were Not Enrolled	x
Subjects Met All Eligibility Criteria and Not Enrolled	x
Subjects Enrolled	86
Subjects Enrolled and Never Treated	0
Subjects in Safety Analysis Set	86
Subjects in Full Analysis Set	xx
Subjects Completed Study Drug	0
Subjects Prematurely Discontinuing Study Drug	xx (x.x%)
Reason for Prematurely Discontinuing Study Drug	
Reason 1	xx (x.x%)
Reason 2	xx (x.x%)
Reason x	xx (x.x%)
Subjects Completed Study	0
Subjects Prematurely Discontinuing Study	xx (x.x%)
Reason for Prematurely Discontinuing Study	
Reason 1	xx (x.x%)
Reason 2	xx (x.x%)
Reason x	xx (x.x%)

2. Defining ARV Regimen at Study Entry

All subjects are expected to enter the study on E/C/F/TAF FDC or FTC/TDF + 3rd agent.

Using the ARV raw dataset, include all prior and/or current ARVs (ARV.INGRED where ARV.CMSCAT = 'Prior ARV' or 'Current ARV'), taken on or up to 2 day prior to first dose date.

When determining the ARV regimen at study entry, please use the following rules:

- The ARV regimen at study entry will be recorded as 3rd Agent + FTC/TDF (note the reversed order, as this is due to clinical trials evaluating novel 3rd agents). When ordering the 3rd Agent medications, use the following order to assign priority:

INGRED	Priority	INGRED	Priority
EFV FTC TDF	1.2	RAL	3.2
EVG COBI FTC TDF	1.3	EFV	4.1
FTC RPV TDF	1.4	ETR	4.2
ATV COBI	2.1	NVP	4.3
DRV COBI	2.2	RPV	4.4
LPV RTV	2.3	ABC 3TC	5.1
ATV	2.4	FTC TDF	5.2
DRV	2.5	ABC	5.3
COBI	2.6	FTC	5.4
RTV	2.7	3TC	5.5
		TDF	5.6

- For all ingredients, replace “_” with “/”
- Make the following replacements to the ingredients:

Replace “DTG/ABC/3TC” with “ABC/DTG/3TC”

Replace “ATV/COBI” with “ATV/co”

Replace “DRV/COBI” with “DRV/co”

Replace “LPV/RTV” with “LPV/r”

- Once the ingredients have been updated and assigned an appropriate priority, transpose the ingredients (by subject) and concatenate each column with a “+” following the priority specified above

To illustrate these rules, suppose a subject is on ATV, RTV, and FTC_TDF. This would translate into “ATV+RTV+FTC/TDF”. If, instead, the subject was on LPV_RTV and FTC_TDF, their regimen would be presented as “LPV/r+FTC/TDF”.

Note: The following data issues should be queried:

- If the subject does not have either EVG/COBI/FTC/TDF or FTC/TDF in their ARV regimen at study entry
- If a subject does not have a 3rd agent (eg, is only identified as being on FTC/TDF)
- If a subject is on RTV but is not *also* on ATV or DRV

The major protocol violations to be used in defining exclusion from the FAS are:

- a) ARV regimen at study entry other than E/C/F/TAF FDC (or FTC/TDF + 3rd agent if currently or previously participated in GS-US-292-1826). Please see above for definition of ARV regimen at study entry.
- b) ARV regimen at study entry for < 3 months. This is defined as ARV regimen starting less than 90 days prior to first dose date.

3. For the nonstudy-drug ARV listing, ARVs which were dosed between the first dose date and the last dose date (inclusive) will be flagged (eg, ^). However, please note, the ARV will not be flagged if any of the following criteria are met:

- a) the medication end date is completely missing and the medication is not ongoing, and the CRF indicates 'Prior ARV'
- b) the medication end date has year only and the year is equal to the year of first dose and the CRF indicates 'Prior ARV'.

4. The precision in reporting numerical values should be as follows:

- a) Raw measurements will be reported the same as the data captured electronically or on the CRFs.
- b) Standard deviation and standard error will be reported to one more significant decimal place than the raw measurement.
- c) Mean, median, minimum, Q1, Q3, maximum, 95% CIs will be reported to the same number of decimal places of the raw measurements.
- d) Exceptions may be considered; for example if more than 4 significant digits are provided for the measurement.

5. AGE is calculated as follows:

- a) Only year is provided for the date of birth (DOB). Use July 1 for the month and day.
- b) AGE (years) is calculated from the number of days between the date of birth (DOB) and Day 1 (first dose date),
- c) Use the SAS INTCK function to determine the number of “1st-of-month days” (eg, January 1st, February 1st, March 1st) between DOB and Day 1 (inclusive),
- d) Divide the result in (b) by 12,
- e) AGE = the integer of the result in (c)

6. In disposition table, the reasons for premature discontinuation are displayed in the order as they appear on the eCRF.

7. Body mass index (BMI)

BMI will be calculated as follows:

$$\text{BMI} = (\text{weight [kg]}) / (\text{height [meters]}^2)$$

Baseline height and weight of the study will be used for this calculation.

8. Last Dose Date of B/F/TAF and Last Study Date

Last Dose Date in ADSL was defined in Section [3.8.1](#).

For subjects with a partial last dosing date of B/F/TAF (ie, month and year of last dose are known), the minimum of (death date, if available), (the latest of the dispensing dates of B/F/TAF bottles, B/F/TAF start dates and end dates (based on EX dataset), and the imputed last dose date [day imputed as 15])} will be used as the final imputed last dose date. However if dispensing date’s month is after last dose date’s month, data query is needed.

Last Study Date is the latest of the study drug start dates and end dates, the clinic visit dates, and the laboratory visit dates, including the 30-day follow-up visit date, for subjects who prematurely discontinued study or who completed study according to the Study Completion eCRF. If study drug start dates or end dates is partially missing (ie, only year and month are known), the day will be imputed as 15 for the purpose of this analysis. If the subject died and the death date is complete (ie, not partial date) and before the imputed last study date, the complete death date should be used as the imputed last study date.

9. Toxicity Grades:

- 1) For toxicity grade summaries, include all postbaseline graded results up to 30 days after the last dose of B/F/TAF, not just those used in by-visit summaries.
- 2) For glucose grading, as specified in SAP Section 7.2.2.1, the treatment-emergent flag cannot be determined for nonfasting glucose (including glucose results without a known fasting status). As a result, these records will be excluded from the “Maximum Treatment-emergent Toxicity Grade” summary in the “Treatment-emergent Laboratory Abnormalities” or “Treatment-emergent Grade 3 or 4 Laboratory Abnormalities” summary tables. In addition, fasting glucose and non-fasting glucose will be listed as two separate laboratory tests in the “Laboratory Abnormalities” and “Grade 3 or 4 Laboratory Abnormalities” listings. Only a maximum postbaseline toxicity flag will be displayed and the treatment-emergent flag will not be displayed for nonfasting glucose as the treatment-emergent flag cannot be determined for nonfasting glucose.

10. Graded Laboratory Abnormalities Summary

The following labels will be used for treatment-emergent laboratory abnormalities and treatment-emergent Grade 3 or 4 laboratory abnormalities summary tables and listings:

Battery	Lab Test Label Used in l-labtox Listing	Toxicity Direction	Lab Test Label Used in t-labtox Table
Hematology	Hemoglobin	Decrease	Hemoglobin (Decreased)
	Neutrophils	Decrease	Neutrophils (Decreased)
	Platelets	Decrease	Platelets (Decreased)
	WBC	Decrease	WBC (Decreased)
Chemistry	Albumin	Decrease	Albumin (Decreased)
	Alkaline Phosphatase	Increase	Alkaline Phosphatase (Increased)
	ALT	Increase	ALT (Increased)
	AST	Increase	AST (Increased)
	Bicarbonate	Decrease	Bicarbonate (Decreased)
	Corrected Calcium	Increase	Corrected Calcium (Hypercalcemia)
	Corrected Calcium	Decrease	Corrected Calcium (Hypocalcemia)
	Creatinine	Increase	Creatinine (Increased)
	Serum Glucose (Fasting)	Increase	Serum Glucose (Fasting, Hyperglycemia)
	Serum Glucose (Fasting)	Decrease	Serum Glucose (Fasting, Hypoglycemia)
	Serum Glucose (Nonfasting)	Increase	Serum Glucose (Nonfasting, Hyperglycemia)
	Serum Glucose (Nonfasting)	Decrease	Serum Glucose (Nonfasting, Hypoglycemia)
	Serum Potassium	Increase	Serum Potassium (Hyperkalemia)
	Serum Potassium	Decrease	Serum Potassium (Hypokalemia)
	Serum Sodium	Increase	Serum Sodium (Hypernatremia)
	Serum Sodium	Decrease	Serum Sodium (Hyponatremia)
	Total Bilirubin	Increase	Total Bilirubin (Hyperbilirubinemia)

Battery	Lab Test Label Used in l-labtox Listing	Toxicity Direction	Lab Test Label Used in t-labtox Table
	Total Cholesterol (Fasting)	Increase	Total Cholesterol (Fasting, Hypercholesterolemia)
	Triglycerides (Fasting)	Increase	Triglycerides (Fasting, Increased)
	LDL (Fasting)	Increase	LDL (Fasting, Increased)
	Urea Nitrogen (BUN)	Increase	Urea Nitrogen (Increased)
	Prothrombin Intl. Normalized Ratio (INR)	Increase	N/A
	Prothrombin Time (PT)	Increase	N/A
Urinalysis	Urine Blood	Increase	N/A
	Urine Glucose	Increase	Urine Glucose (Glycosuria)
	Urine Protein	Increase	Urine Protein (Proteinuria)
	Urine RBC	Increase	Urine RBC (Hematuria, Quantitative)

Note: Prothrombin Intl. Normalized Ratio (INR) and Prothrombin Time (PT) were graded based on the protocol defined toxicity grade scale. The results and toxicity grade will be listed in listing, but not be summarized in lab toxicity summary table. Due to the reflexive nature of the quantitative urine RBC test, results will be combined with the dipstick test of urine blood as described below. General rule is that urine RBC (Quantitative) should always be used first (if available), no matter if it is collected at the same time of Urine Blood (Dipstick) or not. The combined Urine RBC (hematuria, Quantitative or Dipstick) toxicity grade will be used for “Maximum treatment emergent toxicity grade” summary.

Is Post-BL Urine RBC (Quant.) Result Available?	Is BL Urine RBC (Quant.) Result Available?	Is Post-BL Urine Blood (Dipstick) Result Available?	Is BL Urine Blood (Dipstick) Result Available?	How to Determine Treatment-Emergent Toxicity for “Urine RBC (Hematuria, Quantitative or Dipstick)”
Yes	Yes			Compare post BL Urine RBC (Quant.) toxicity grade to BL Urine RBC (Quant.) toxicity grade. If post BL toxicity is greater than BL toxicity, then treatment emergent
Yes	No			Treatment emergent. Use post BL Urine RBC (Quant.) toxicity grade
No		Yes	Yes	Compare posy BL Urine Blood (Dipstick) toxicity grade to BL Urine Blood (Dipstick) toxicity grade. If post BL toxicity grade is greater than BL toxicity, then treatment emergent
No		Yes	No	Treatment emergent. Use post BL Urine Blood (Dipstick) toxicity grade
No		No		Do not count subject in the denominator for “Urine RBC (Hematuria, Quantitative or Dipstick)”

11. Renal related laboratory evaluation

- 1) Unit conversion for renal safety tests derived from related tests with conventional units
 - a) Urine RBP (ug/L) to creatinine (mg/dL) ratio: $1 \text{ (ug/L)} / \text{(mg/dL)} \times 100 \text{ x ug/g}$
 - b) Urine Beta-2-microglobulin (mg/L) to creatinine (mg/dL) ratio: $1 \text{ (mg/L)} / \text{(mg/dL)} \times 10^5 \text{ ug/g}$
 - c) UP (mg/L) to creatinine (mg/dL) ratio: $1 \text{ (mg/dL)} / \text{(mg/dL)} \times 1000 \text{ x mg/g}$

Calculation of ratios:

To calculate laboratory ratios (eg, urine RBP to creatinine ratio), the lab value of each test in the ratio needs to be from the same accession number; if any test value used for the ratio calculation from the same accession number is missing, then the ratio is not calculable (ie, missing). UPCR is not calculated if the urine protein value used for the ratio calculation from the same accession number is under the lower limit of quantification (ie, $< 4.0 \text{ mg/dL}$).

For the combined category of UP and UPCR: UP and UOCR should be merged together based on the subject identifier and accession number. At each visit, select the nonmissing UP value in the analysis window. Once the UP record is selected, then the UPCR with the same accession number is selected. If the UP value is $< 4.0 \text{ mg/dL}$ then the corresponding UPCR value will be missing. Subjects will be classified as “UP $< 4.0 \text{ mg/dL}$ ” if UP $< 4.0 \text{ mg/dL}$ (ie, UPCR should not be calculated for this record); Subject will be classified as “UPCR $\leq 200 \text{ mg/g}$ ” if UP $\geq 4.0 \text{ mg/dL}$ and UPCR $\leq 200 \text{ mg/g}$; Subject will be classified as “UPCR $> 200 \text{ mg/g}$ ” if UP $\geq 4.0 \text{ mg/dL}$ and UPCR $> 200 \text{ mg/g}$; Otherwise, subject will be classified as “Missing”.

12. Chronic non-ARV medications at baseline

A chronic non-ARV medication at baseline is defined as

- a) a concomitant medication with start date on or prior to Study Day 1 (or completely missing start date) and either “ongoing” or stop date after Study Day 1. For partial start dates, if the month and year (or year, if month is not recorded) of the start date is equal to the month and year of Study Day 1, then the medication is defined as a baseline medication. For partial stop dates, if the month and year (or year, if month is not recorded) of the stop date is equal to the month and year of Study Day 1, then the medication is defined as a baseline medication.
- b) with route “ORAL” or route “RESPIRATORY (INHALATION)”
- c) with a duration of > 30 days. Duration is defined as stop date minus start date plus one. For partial start and stop dates, if the month and year are the same, then the duration is assumed to be < 30 days. Otherwise, if the months are different and the years are the same, then the duration is assumed to be > 30 days. If both start and stop dates have year only and the years are the same, the duration is assumed to be < 30 days. If both start and stop dates have year only and the years are different, the duration is assumed to be > 30 days.

13. Smoking Status at baseline

Smoking status at baseline (ie, never smoker, former smoker, and current smoker) will be summarized as part of the baseline disease characteristics. How to classify a subject as never, former, or current smoker at baseline is specified as follows:

- a) First, select only records with Type of Substance Use “Cigarettes” or “Cigars”. Records with *Type of Substance Use* “Other” (including chew tobacco, e-cigarettes, etc) will not be considered as smoking.
- b) Second, for each selected substance use record, flag whether it is “Prior”, “Present”, or “Post” relative to the first dose date according to the Algorithm below.
- c) Finally, (1) the subject will be flagged as “Never smoker”, if the subject has no record with Type of Substance Use “Cigarettes” or “Cigars” or all selected records have a flag of “Post”; (2) the subject will be flagged as a “Former” smoker, if any selected records has a flag of “Prior” and no record of “Present”; (3) Otherwise, the subject will be flagged as a “Current” smoker, if any selected records has a flag of “Present”.

	Selected Substance Use Records							
Prior	No	No	Yes	Yes	Yes	No	No	Yes
Present	No	No	No	No	Yes	Yes	Yes	Yes
Post	No	Yes	No	Yes	No	No	Yes	Yes
Smoking Status	Never	Never	Former	Former	Current	Current	Current	Current

Algorithm to flag whether a selected record is “Prior”, “Present”, or “Post” relative to the first dose date:

- 1) the start and stop dates of the selected record are not completely missing (ie, at least year is known) or the start date is not missing and record is ongoing. The completed start or stop dates will be used to compare with the first dose date whenever possible. Otherwise, the month and year (or year alone if month is not recorded) of the start or stop dates will be used to compare with the first dose date when the start or stop date of the selected record is incomplete.
 - a) The record is flagged as “Prior”, if the stop date is before (<) the first dose date;
 - b) The record is flagged as “Present”, if the start date is on or before (\leq) the first dose date and the stop date is on or after (\geq) the first dose date, or the selected record is marked as ongoing and the start date is on or before (\leq) the first dose date;
 - c) The record is flagged as “Post”, if the start date is after the first dose date;

- 2) the start date of the selected record is completely missing. We assume that the start date is before the first dose date, the stop date (or the month and/or year of the stop date, if stop date is incomplete) will be used to determine whether the selected record is “Prior” or “Present” as follows.
 - a) The record is flagged as “Prior”, if the stop date is before ($<$) the first dose date or the stop date is completely missing and the record is not marked as ongoing.
 - b) The record is flagged as “Present”, if the stop date is on or after (\geq) the first dose date or the selected record is marked as ongoing.
- 3) the start date of the selected record is before ($<$) the first dose date, but the stop date is completely missing and the record is not marked as ongoing. We assume that the end date is before the first dose date, the record is flagged as “Prior”.
- 4) The start date of the selected record is on or after the first dose date, but the stop date is completely missing and the record is not marked as ongoing. This is a data issue, should be queried first. However, this record is flagged as “Present” if the start date is on the first dose; this record is flagged as “Post” if the start date is after the first dose.

14. Figures

For figures, if at a visit where n (sample size) is < 5 , data will not be displayed at that visit in the figure, but all data will be included in the corresponding table summary.

GS-US-380-4449 Final SAP

ELECTRONIC SIGNATURES

Signed by	Meaning of Signature	Server Date (dd-MMM- yyyy hh:mm:ss)
PPD	Biostatistics eSigned	20-Aug-2020 15:31:58
PPD	Medical Affairs eSigned	21-Aug-2020 23:21:05
